15.3.15. Part 2–Cycle 10+, Day 1 (P2-C10+D1; Week 61+) ± 7 days

The procedures described below are performed at P2-C10D1 ± 7 days and every 12 weeks thereafter (eg, P2-C13, P2-C16).

To be performed within (±) 7 days of the visit:

- MRI of the affected joint (with local assessment of progression status);
- Third-party blinded range-of-motion assessment of the affected joint.

To be performed *before* any invasive procedures:

- Vital signs, including blood pressure, pulse rate, and oral temperature;
- PRO instruments, in the following order:
 - BPI Worst Pain NRS Item
 - Worst Stiffness NRS item
 - PROMIS Physical Function Scale
 - EQ-5D-5L

Other procedures to be performed:

- Dispense study treatment bottles.
- Review outpatient PRO instruments;
- AE assessment;
- Concomitant medications, including analgesics;
- Treatment compliance assessment;
- Physical examination;
- Clinical laboratory tests — serum chemistry, hematology, liver function, serum pregnancy testing (if applicable);

- Analgesic use assessment;

15.3.16. Post-Treatment Visit (Part 2)

The Post-treatment Visit is scheduled 28 ± 7 days after the last dose of study treatment.

To be performed within (\pm) 7 days of the visit:

- MRI of the affected joint (with local assessment of progression status);
- Third-party blinded range-of-motion assessment of the affected joint.

To be performed *before* any invasive procedures:

- Vital signs, including blood pressure, pulse rate, and oral temperature;
- 12-lead ECG;
- PRO instruments (if not done within the last 30 days), in the following order:
 - BPI Worst Pain NRS Item
 - Worst Stiffness NRS item
 - PROMIS Physical Function Scale
 - EQ-5D-5L

Other procedures to be performed:

- Review outpatient PRO instruments;
- AE assessment;
- Concomitant medications, including analgesics;
- Treatment compliance assessment;
- Analgesic use assessment;
- Weight;
- Physical examination;
- ECHO or MUGA scanning (only if >3 months have elapsed since the previous scan);
- Clinical laboratory tests — serum chemistry, hematology, coagulation, liver function, hormone levels, serum pregnancy testing (as applicable), urinalysis;
- Surgical Assessment Questionnaire;
- For subjects terminating the study because of progression, document if they plan to undergo any new PVNS/GCT-TS therapy, including surgery, during the 28-day period (\pm 7 days) after their last dose of study treatment.
- For subjects who undergo surgical resection of the tumor within 12 weeks of the last dose of study treatment, refer to Section 15.4 for collection of surgery related data.

15.3.17. End-of-Study or Early Termination Visit

The End-of-Study/Early Termination Visit is scheduled 12 weeks \pm 7 days after the last dose of study treatment or before any new PVNS/GCT-TS therapy, including surgery, whichever occurs first.

To be performed within (\pm) 7 days of the visit:

- MRI of the affected joint (with local assessment of progression status);

Other procedures to be performed:

- Clinical laboratory tests - serum pregnancy testing (if applicable);
- AE assessment;
- Concomitant medications;
- Ask the subject if s/he has begun any new PVNS/GCT-TS therapy, including surgery; For subjects who undergo surgical resection of the tumor within 12 weeks of the last dose of study treatment, refer to Section 15.4 for collection of surgery related data.
- For other subjects, terminate the subject from the study.

15.4. Detailed Study Procedures by Visit — Surgical Outcome

For subjects who undergo surgical resection of the tumor within 12 weeks of the last dose of study treatment, they will remain on the study and follow a different study visit schedule to

obtain data on the surgical procedure and its outcome. There is no need to have the End-of-Study visit.

If a subject has surgery within 4 weeks of the last dose of study treatment, the subject does not need to have the Post-Treatment Visit evaluations per Section 15.2 and Section 15.3, but will need to have the safety lab tests (blood chemistry, hematology, liver function tests, coagulation tests, urinalysis, and serum pregnancy test) and an ECG performed at least 7 days after the last dose of study treatment, but prior to surgery.

If a subject has surgery after 4 weeks of the last dose of study treatment, the subject should have the Post-Treatment Visit evaluations per Section 15.2 and Section 15.3.

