The timing and nature of post-treatment assessments are summarized in [Figure 3.2](#). Subjects who end their study participation with no documented disease progression will undergo: (i) the 28 Day Post-treatment Visit assessment *with* an MRI 28 ± 7 days after their last dose of study treatment; and (ii) a final MRI 12 weeks ± 7 days after their last dose of study treatment or before any new PVNS/GCT-TS therapy, including surgery, whichever occurs first (the “Part 1 End-of-Study/12 Week Post-Treatment”). Subjects who wish to continue onto the open label part of this study (Part 2) will be unblinded after completion of the end of Part 1 assessments and those on placebo will be discontinued- they will not have the 28 Day Post-treatment and End-of-Study Visit assessments. The study will end with the last subject last visit. Subjects who complete Part 2 and enter a separate protocol to continue receiving pexidartinib will not be scheduled for the Post-treatment and End-of-Study Visits. Subjects who terminate the study with documented progression will undergo a post-treatment assessment (the 28 Day “Post-treatment Visit”; see [Section 15.2.17](#) and [Section 15.3.16](#)) *without* an MRI 28 ± 7 days after their last dose of study treatment or before any new PVNS/GCT-TS therapy, including surgery, whichever occurs first.

Subjects are allowed to undergo surgical resection of their tumor after the completion of Part 1. For subjects who undergo surgical resection within 12 weeks after their last dose of study treatment, they will not have the End-of-Study Visit assessments but will follow a separate visit schedule after the decision of surgery is made. The surgery is recommended to be performed 1-3 weeks after the last dose of study treatment. Details of the surgery and its short and long term outcome will be collected. Data collection for the surgery and its outcome may continue in a separate protocol.

Figure 3.2: Post-treatment Assessments Vary With Reason for Study Withdrawal*

* Effective 30 Sep 2016, subjects on placebo are no longer allowed into Part 2 to receive open-label pexidartinib. Subjects who wish to continue onto the open label part of this study (Part 2) will be unblinded after completion of the end of Part 1 assessments and those on placebo will be discontinued- they will not have the 28 Day Post-treatment and End-of-Study Visit assessments.

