6.4.11. Surgical Data and Outcome Follow-up

At or after Week 25 evaluation, subjects may be considered for surgery to remove the tumor. The surgery is recommended to be performed 1-3 weeks after the last dose of the study treatment. After completion of the end of Part 1 assessments (Part 1 Completion visit/Early Termination visit), subjects who wish to continue onto the open label part of this study (Part 2) will be unblinded and those on placebo will be discontinued and will not need to have surgical data follow-up.

Detailed information about the surgery will be collected, including but not limited to:

- Reasons of the surgery
- Planned surgical procedure and actual surgical procedure performed
- Surgical margin
- Copies of surgical report and pathology report, if available
- Surgery complications such as infection, delayed healing

Surgically resected tumor samples will be collected for evaluation of study treatment effects on tumor cells.

Before the surgery is performed, the subject should have an additional visit for ROM and PRO (pain and stiffness scores, PROMIS questionnaire) evaluation, if these are not done within 6 weeks prior to the surgery. Subjects do not need to have the End-of-Study visit if a decision has been made to have surgical resection of the tumor under study treatment.

At 4 months (+/- 2 weeks) after the surgery, the subject should have a visit for MRI scan of the tumor affected joint, ROM and PRO (pain and stiffness scores, PROMIS questionnaire) evaluations. After this visit, the subject should be followed for disease recurrence (defined as the need for any new therapeutic intervention of TGCT) at 8, 12, 18 and 24 months after surgery. Such follow-up can be performed via phone contact with the subject.

Subjects who undergo surgery may be rolled into a separate protocol for surgery and its outcome data collection.

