6.4.17. Adverse Events

Adverse events will be monitored throughout the study. Adverse events and SAEs will be monitored and recorded in the source documents and eCRFs from the time the subject signs informed consent through the subject's Post-Treatment Visit 28 days (\pm 7 days) after the last dose of study treatment. Adverse events (including clinically significant changes in laboratory results, ECHO results, and hormone testing results) should be monitored until they are resolved or are determined to be due to a subject's stable or chronic condition or intercurrent illness(es). If an AE remains unresolved at the conclusion of the study, the Investigator should follow the AE until s/he deems it to be resolved, stable, or not expected to worsen per medical judgment (eg, resolved with sequelae). Definitions, documentation, and reporting of AEs are described in detail in Section 9.

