7.10.1. Analysis of Treatment-emergent Adverse Events

TEAEs are AEs that occur, having been absent before the first dose of study treatment, or have worsened in severity after the initiating the study treatment. TEAEs will be coded using MedDRA and assigned grades based on version 4.0 of the National Cancer Institute's Common Terminology Criteria for Adverse Events (NCI CTCAE). The number and percentage of subjects reporting TEAEs will be tabulated by the worst CTCAE grade, SOC, and PT, with a breakdown by data set (Section 7.10). Similarly, the number and percentage of subjects reporting treatment-emergent SAEs will be tabulated, as well as TEAEs leading to discontinuation of study treatments.

A by-subject AE (including treatment-emergent) data listing including but not limited to verbatim term, preferred term, system organ class, CTCAE grade, and relationship to study treatment will be provided. Deaths, other SAEs, and other significant AEs, including those leading to discontinuation of study treatments, will be listed.

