15.2.16. Part 1 Completion visit/Early Termination Visit (Week 25) \pm 7 days

For subjects continuing to Part 2, see Section [15.3.1](#) instead.

To be performed within the 7-day period *before* the visit:

- ECHO or MUGA scanning;
- MRI of the affected joint (with local assessment of progression status);
- Third-party blinded range-of-motion assessment of affected joint.

To be performed *before* any invasive procedures:

- Vital signs, including blood pressure, pulse rate, and oral temperature;
- 12-lead ECG.
- PRO instruments, in the following order:
 - BPI Worst Pain NRS Item;
 - Worst Stiffness NRS item;
 - PROMIS Physical Function Scale;
 - Patient Global Rating of Concept item for carrying out every day physical activities;
 - EQ-5D-5L;
 - Patient Global Impression of Change item for tumor-related stiffness.

Other procedures to be performed:

- Review outpatient PRO instruments;
- AE assessment;
- Concomitant medications, including analgesics;
- HCRU and productivity.
- Treatment compliance assessment;
- Analgesic use assessment;

- Weight;
- Physical examination;
- Clinical laboratory tests — serum chemistry, hematology, coagulation, liver function, hormone levels, serum pregnancy testing (as applicable), urinalysis;
- Surgical Assessment Questionnaire.
- For subjects who undergo surgical resection of the tumor within 12 weeks of the last dose of study treatment, refer to Section 15.4 for collection of surgery related data. If a subject has surgery within 4 weeks of the last dose, the subject does not need to have the 28 Day Post-Treatment Visit evaluations. However, if a subject has surgery after 4 weeks of the last dose, the subject should have the 28 Day Post-Treatment Visit evaluations. None of these subjects need to have the End-of-Study Visit.

As of 30 Sep 2016, subjects who wish to continue onto the open label part of this study (Part 2) will be unblinded after completion of the end of Part 1 assessments (Part 1 Completion visit/Early Termination visit) and those on placebo will be discontinued; subjects on pexidartinib in Part 1 may continue into Part 2 to continue to receive pexidartinib. Subjects who discontinue Part 1 early, should complete the end of Part 1 assessments (Part 1 Completion visit/Early Termination) at or before the time of their last treatment (MRI or range of motion assessments do not need to be repeated, if completed in the previous 28 days).

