15.4.1. Four weeks Prior to Surgery

For subjects undergoing surgical resection, the following procedures are performed within the 4-week period *before* surgery:

- MRI of the affected joint (Only perform if not done within 12 weeks prior to the surgery)
- Third-party blinded range-of-motion assessment of the affected joint.
- PRO instruments, in the following order:
 - BPI Worst Pain NRS item;
 - Worst Stiffness NRS item;
 - PROMIS Physical Function Scale;
- Collection of SAEs (Note: hospitalization for the surgery is not considered as SAE)
- Reasons for surgery

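### Surgery within 4 weeks of the last dose waives the visit that ends AE recording, and the surgical schedule that replaces it lists SAEs only

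*Combined protocol and SAP*

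**What the plan says.** **AE recording period.** Section 6.4.17 has AEs and SAEs recorded "from the time the subject signs informed consent through the subject's Post-Treatment Visit 28 days" (± 7 days) after the last dose. Section 9.1 sets the same end point. Neither section makes an exception for subjects who go to surgery.

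**Timing of surgery.** Section 6.4.11 states: "The surgery is recommended to be performed 1-3 weeks after the last dose of the study treatment". Section 3.1 and the synopsis say the same.

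**Waiver.** Section 15.4 sets the rule for early operations: "surgery within 4 weeks of the last dose of study treatment, the subject does not need to have the Post-Treatment Visit evaluations". The Part 1 visit list (Section 15.2.16) repeats it: "If a subject has surgery within 4 weeks of the last dose, the subject does not need to have the 28 Day Post-Treatment Visit evaluations". Section 15.3.14 and footnote a of Table 15.4 carry the same rule.

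**What replaces the visit.** The exempted subjects stay on study. They need chemistry, hematology, liver, coagulation, urine and (serum) pregnancy tests and an ECG, at least 7 days after the last dose and before the operation (Section 15.4; Table 15.4, footnotes a and d). For events, Section 15.4.1 lists "Collection of SAEs (Note: hospitalization for the surgery is not considered as SAE"). Sections 15.4.2 and 15.4.3 also name SAEs only. Table 15.4 has an SAE row and, at 4 months, a surgical-complications row, but no general AE row.

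**Withdrawal rule.** Section 4.2.2 asks that the post-treatment procedures be done 28 ± 7 days after the last dose and before any new therapy, surgery included.

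**The concern.** The plan ends AE recording at a named visit and then releases one group from that visit. The release is not a rare exception, because the recommended surgery time lies wholly inside the 4-week limit. For these subjects the recording period ends at a visit they need not attend, and the schedule in its place asks about serious events only.

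A site that follows Section 15.4 to the letter has no scheduled occasion after surgery to ask about non-serious events in the rest of the 28-day period. A site that follows Sections 6.4.17 and 9.1 will record them anyway. What is at stake is complete and uniform off-drug AE ascertainment in operated subjects, in a programme whose protocol treats delayed and protracted toxicity as important.

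**Working it through.** There is no design figure to reproduce. The check is a count of days from the last dose (day 0) and a comparison of passages.

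**Inputs**
- Recommended surgery: 1 to 3 weeks, so days 7 to 21 (Sections 3.1, 6.4.11).
- Waiver limit: 4 weeks, so day 28 (Section 15.4).
- Post-Treatment Visit: day 28 ± 7, so days 21 to 35 (Sections 6.4.17, 9.1).
- Replacement safety panel and ECG: from day 7 up to surgery (Section 15.4).
- Next dated visit after surgery: 4 months ± 2 weeks (Section 15.4.3).

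**Step 1: does the waiver cover the recommended range?** Day 21 is before day 28, so it covers all of it.

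**Step 2: time from surgery on day s to the end of the AE period.** The gap to day 28 is 28 − s, and to the end of the visit window 35 − s.

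| Surgery day | Gap to day 28 | Share of 28 days | Gap to day 35 | Days available for the safety panel |
|---|---|---|---|---|
| 7 | 28 − 7 = 21 | 75% | 28 | day 7 only |
| 14 | 28 − 14 = 14 | 50% | 21 | 7 to 14 |
| 21 | 28 − 21 = 7 | 25% | 14 | 7 to 21 |

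**Step 3: next dated contact.** Four months is about 4 × 30.4 ≈ 122 days. Surgery on day 7 puts the earliest visit at 7 + 122 − 14 = day 115. Surgery on day 21 puts the latest at 21 + 122 + 14 = day 157. That visit lists SAEs and surgical complications and has no safety laboratory tests. The step during or shortly after surgery (Section 15.4.2) comes sooner, but it has no date and lists SAEs only.

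**Step 4: the passages side by side**

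| | Sections 6.4.17 and 9.1 | Sections 15.4 to 15.4.3, Table 15.4 |
|---|---|---|
| Events | all AEs and SAEs | SAEs only |
| End of recording | Post-Treatment Visit | visit waived; no other end point given |
| Safety tests after surgery, to day 28 ± 7 | at the Post-Treatment Visit | none scheduled |

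**Step 5: Section 4.2.2.** Its procedures belong in days 21 to 35 and before surgery. With surgery on days 7 to 21, only day 21 touches that window. Section 4.2 says subjects operated on after Part 1 are not considered discontinued, so Section 4.2.2 may not be meant for them. Yet it also speaks of subjects who stop treatment to have surgery, and the text does not settle the matter.

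**The case against.** The strongest reply is that nothing is switched off. Sections 6.4.17 and 9.1 still bind for these subjects. Section 9.1 tells the investigator to look for AEs at each visit, to record clinically significant laboratory values as AEs, and to follow open AEs until they resolve or stabilize. Potential Hy's Law cases are reported within 24 hours whether serious or not (Section 9.3.1). Raised liver tests trigger more frequent monitoring (Tables 15.2 and 15.3). Surgical complications are collected.

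All of that stands, and it means non-serious events remain recordable. It does not supply a visit: the general duty in Section 9.1 attaches to visits, and after the undated perioperative step none is scheduled before 4 months.

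Three stronger readings are tempting, and the documents do not support them.

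- **That liver tests are lost in the 28-day window.** They are not. Section 15.4 requires a panel with liver tests between day 7 and surgery. Only a scheduled test after surgery is absent.
- **That off-drug AE follow-up differs by exit route in a way that singles out operated subjects.** Placebo subjects unblinded and discontinued after Part 1, and subjects who move to the separate protocol, also skip the post-treatment visits. The 12-week visit lists an AE assessment, but Sections 6.4.17 and 9.1 end recording at 28 ± 7 days, so it is unclear whether new events are collected there.
- **That the treatment-emergent definition needs a day-28 cut-off.** Section 7.10.1 gives no end date ("TEAEs are AEs that occur, having been absent before the first dose of study treatment, or have worsened in severity"), but Section 7.4 defers further detail to the SAP. A cut at day 28 would drop events on days 29 to 35, inside the protocol's own visit window.

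**Conclusion.** The point holds as an inconsistency that is cheap to repair. Surgery at the recommended time waives the visit that closes AE recording, and the replacement schedule names SAEs only. From surgery to day 28 ± 7, these subjects have no scheduled all-AE assessment and no scheduled safety laboratory test. The gap to day 28 is 7 to 21 days for surgery on day 21 back to day 7.

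This assumes that sites follow Section 15.4 and Table 15.4 as written and operate within the recommended 1 to 3 weeks. The number of subjects affected is not stated, and no TEAE summary is planned for operated subjects alone. The effect on any TEAE table therefore cannot be sized, and understated incidence should not be asserted. The primary and secondary efficacy analyses are not touched.

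**What to change.** 1. In Sections 15.4.1 to 15.4.3 and Table 15.4, replace the SAE-only entry with collection of all AEs through 28 ± 7 days after the last dose, and SAEs thereafter. This brings the surgical schedule into line with Sections 6.4.17 and 9.1.
2. Add one AE contact at last dose + 28 (± 7) days for subjects whose Post-Treatment Visit is waived. It can be by phone, as the protocol already allows for recurrence follow-up (Section 6.4.11; Table 15.4, footnote f). State that this contact ends their AE recording period.
3. Reconcile Section 4.2.2 with Section 15.4 at the same time, saying whether it applies to subjects who go to surgery.

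The cost is protocol wording and one call per operated subject. The drawback is that some non-serious postoperative events will enter the AE data. They should be identifiable as having started after surgery, so that they can be read separately from events that preceded it.

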15.4.1. Four weeks Prior to Surgery

For subjects undergoing surgical resection, the following procedures are performed within the 4-week period *before* surgery:

- MRI of the affected joint (Only perform if not done within 12 weeks prior to the surgery)
- Third-party blinded range-of-motion assessment of the affected joint.
- PRO instruments, in the following order:
 - BPI Worst Pain NRS item;
 - Worst Stiffness NRS item;
 - PROMIS Physical Function Scale;
- Collection of SAEs (Note: hospitalization for the surgery is not considered as SAE)
- Reasons for surgery

15.4.2. During or shortly after Surgery

- Surgical procedures and findings
- Tumor sample submission
- Collection of SAEs

15.4.3. 4 Months (± 2 weeks) after Surgery

- MRI of the affected joint
- Third-party blinded range-of-motion assessment of the affected joint.
- PRO instruments, in the following order:
 - BPI Worst Pain NRS item;
 - Worst Stiffness NRS item;
- Collection of SAEs (Note: hospitalization for the surgery is not considered as SAE)
- Disease Recurrence

15.7. PROMIS Physical Function Scale

PROMIS Item Bank v. 1.2 – Physical Functioning (Lower Extremity)

Please respond to each item by marking one box per row.

		Without any difficulty	With a little difficulty	With some difficulty	With much difficulty	Unable to do
PFA23	Are you able to go for a walk of at least 15 minutes?	 5	 4	 3	 2	 1
PFA16r1	Are you able to dress yourself, including tying shoelaces and buttoning up your clothes?	 5	 4	 3	 2	 1
		Not at all	Very little	Somewhat	Quite a lot	Cannot do
PFB54	Does your health now limit you in going OUTSIDE the home, for example to shop or visit a doctor's office?	 5	 4	 3	 2	 1
PFA4	Does your health now limit you in doing heavy work around the house like scrubbing floors, or lifting or moving heavy furniture?	 5	 4	 3	 2	 1
		Without any difficulty	With a little difficulty	With some difficulty	With much difficulty	Unable to do
PFA12	Are you able to push open a heavy door?	 5	 4	 3	 2	 1
PFA14r1	Are you able to carry a heavy object (over 10 pounds/5 kg)?	 5	 4	 3	 2	 1
		Not at all	Very little	Somewhat	Quite a lot	Cannot do
PFB1	Does your health now limit you in doing moderate work around the house like vacuuming, sweeping floors or carrying in groceries?	 5	 4	 3	 2	 1
PFA5	Does your health now limit you in lifting or carrying groceries?	 5	 4	 3	 2	 1
		Without any difficulty	With a little difficulty	With some difficulty	With much difficulty	Unable to do
PFA21	Are you able to go up and down stairs at a normal pace?.....	 5	 4	 3	 2	 1
PFA42	Are you able to carry a laundry basket up a flight of stairs?	 5	 4	 3	 2	 1
PFA10	Are you able to stand for one hour?	 5	 4	 3	 2	 1

		Without any difficulty	With a little difficulty	With some difficulty	With much difficulty	Unable to do
		Not at all	Very little	Somewhat	Quite a lot	Cannot do
PFA3	Does your health now limit you in bending, kneeling, or stooping?	 5	 4	 3	 2	 1
		Without any difficulty	With a little difficulty	With some difficulty	With much difficulty	Unable to do
PFA13	Are you able to exercise for an hour?	 5	 4	 3	 2	 1

PROMIS Item Bank v. 1.2 – Physical Functioning (Upper Extremity)

Please respond to each item by marking one box per row.

		Without any difficulty	With a little difficulty	With some difficulty	With much difficulty	Unable to do
PFB34	Are you able to change a light bulb overhead?.....	 5	 4	 3	 2	 1
PFA16r1	Are you able to dress yourself, including tying shoelaces and buttoning up your clothes?	 5	 4	 3	 2	 1
		Not at all	Very little	Somewhat	Quite a lot	Cannot do
PFB54	Does your health now limit you in going OUTSIDE the home, for example to shop or visit a doctor’s office?	 5	 4	 3	 2	 1
PFA4	Does your health now limit you in doing heavy work around the house like scrubbing floors, or lifting or moving heavy furniture?	 5	 4	 3	 2	 1
		Without any difficulty	With a little difficulty	With some difficulty	With much difficulty	Unable to do
PFA12	Are you able to push open a heavy door?	 5	 4	 3	 2	 1
PFB28r1	Are you able to lift 10 pounds (5 kg) above your shoulder?.....	 5	 4	 3	 2	 1
PFA14r1	Are you able to carry a heavy object (over 10 pounds/5 kg)?	 5	 4	 3	 2	 1
		Not at all	Very little	Somewhat	Quite a lot	Cannot do
PFB1	Does your health now limit you in doing moderate work around the house like vacuuming, sweeping floors or carrying in groceries?	 5	 4	 3	 2	 1
PFA5	Does your health now limit you in lifting or carrying groceries?	 5	 4	 3	 2	 1
		Without any difficulty	With a little difficulty	With some difficulty	With much difficulty	Unable to do
PFA42	Are you able to carry a laundry basket up a flight of stairs?	 5	 4	 3	 2	 1
PFA13	Are you able to exercise for an hour?	 5	 4	 3	 2	 1

